## Objectives

To the best of our knowledge, there has only been one large population-based study assessing psychosocial comorbidities in vitiligo compared to those without the condition.[17] This study was limited only to exploring major depressive disorder (MDD, also termed recurrent depressive disorder) and used an unvalidated case definition for MDD. There have been no large-scale population studies looking at the association between vitiligo and depressive episodes (not meeting the criteria for MDD), anxiety, social phobias and other potential psychological complications of vitiligo. No current study explores the relationship with ethnicity and psychological outcomes or the associations between vitiligo location and a broader range of psychological outcomes beyond MDD. The aim of this study is therefore to fill this evidence gap.

We will conduct a large population-based study in the UK to determine the risks of comorbid mental health conditions (including depression, anxiety and other potential psychological complications of vitiligo) in people with vitiligo compared to control and to evaluate whether the relative risks may vary by different ethnicity. Reliable population-based estimates of the psychological burden associated with vitiligo are important to gain a better understanding of the condition and to ensure patients of different characteristics are provided with appropriate psychological support following diagnosis.

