The eligible vitiligo cases will comprise all incident cases of vitiligo over the last 15 years (2004-2020). Sociodemographic details will be extracted for all these cases and matched controls (described below). Sociodemographic data will comprise age group, gender, ethnicity, and socioeconomic status. Ethnicity will be categorised as follows to be consistent with the UK official census categories: White, Asian, Black African/Caribbean, Mixed, and Other. The index of multiple deprivation (IMD) will be used as a measure of socioeconomic status. This is derived from postcode at the point of data extraction and is available for nearly all patients contributing data.

Each incident case of vitiligo will be matched with an unaffected control (people without vitiligo at the date of matching) using propensity score matching (matching on the sociodemographic

variables list above and matching within primary care practice where numbers allow). The mental health conditions proposed to be examined are listed in table 2.

In addition, we will also explore whether the presence of a mental health condition at vitiligo diagnosis is related differences in service utilisation/management. We will describe the potential association between the presence of a mental health condition at vitiligo diagnosis and whether this is associated with increased primary care visits or an increased chance of a secondary care referral to dermatology. We will compare primary care visits and secondary care referral rates over the first year after diagnosis in those with a depressive illness or anxiety disorder at baseline to those without using Cox proportional hazards models adjusted for sociodemographic factors and other potential confounders. We will also report the overall primary care visit frequency and secondary care referral rate for comparison.

Condition	Description
Primary outcomes	
Depression	Recurrent depressive disorder or treated depressive episode
Anxiety	Non-phobia related anxiety episodes or disorder
Secondary outcomes	
Time off work for illness	Issue of a Med 3 certificate of fitness for work – indicating time off work for illness or other coded evidence of time off work
Unemployment	Any primary care coded evidence of unemployment
Social phobia	Diagnosis of social phobias including agoraphobia
Adjustment disorder	Diagnosis of adjustment disorder

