## Statistical methods

Standard descriptive statistics (mean, standard deviations, etc) will be used to describe the characteristics of the study cohort. The study will report the baseline prevalence (odds ratio) and incidence (hazard ratio) for each mental health condition in the vitiligo cases compared with controls. These outcomes will be compared between cases and controls in subgroups by gender and ethnicity. Within the vitiligo cohort the relationship between disease characteristics and the primary outcomes will be examined. Statistical significance for analyses will be reported using P values and 95% confidence intervals as appropriate.

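### Propensity-score matching does not require a case and its control to share gender or ethnicity, yet the plan compares cases with controls within gender and ethnicity subgroups

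*Protocol*

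**What the plan says.** All references are to the Protocol.

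- **Methods, Study design, candidate variables:** "Sociodemographic data will comprise age group, gender, ethnicity, and socioeconomic status". Ethnicity has five levels: "White, Asian, Black African/Caribbean, Mixed, and Other". Deprivation is measured by the IMD.
- **Methods, Study design, matching:** "Each incident case of vitiligo will be matched with an unaffected control", one control per case as worded, "using propensity score matching (matching on the sociodemographic" variables just listed, and "matching within primary care practice where numbers allow". Same practice is the only preference stated. No patient characteristic has to agree exactly.
- **Statistical methods:** odds ratios for baseline prevalence and hazard ratios for incidence, and then: "These outcomes will be compared between cases and controls in subgroups by gender and ethnicity".
- **Objectives:** the study is to "evaluate whether the relative risks may vary by different ethnicity".

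The only covariate-adjusted model named is the Cox model for service use under Study design. That model compares people with vitiligo by baseline mental health and is not a case-control comparison.

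**The concern.** A propensity score reduces several characteristics to one number. Two people with the same score can differ in ethnicity, sex and age group at once. Matching on the score aims at balance across the whole matched set; it does not pair like with like.

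This matters when the data are split. If a case and its control belong to different ethnic groups, the pair is broken in the ethnicity analysis, and the case is compared with controls chosen for other cases. The same applies to gender. The same-practice preference narrows the pool most for a minority-ethnic case in a mainly White practice, and those are the groups on which the ethnicity aim depends. If control selection left a small ethnic stratum with a different age or sex mix in cases and controls, that could be taken for a difference in relative risk by ethnicity.

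**Working it through.** The protocol gives no sample size, event count or matching diagnostic here, so there is no figure to reproduce. The check has three steps. Apart from the practice and record counts, every simulation input below is an assumption.

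**1. Equal scores do not imply equal characteristics.** Take an illustrative main-effects score on the log scale, with age-group terms 0, 0.20, 0.35, 0.45, 0.50, 0.40, 0.25, 0.10 for groups 1 to 8; ethnicity terms 0 (White) and 0.40 (Black); and a sex term of 0.10.

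- Black, age group 1: 0 + 0.40 = 0.40. White, age group 6: 0.40 + 0 = 0.40. Same score, different ethnicity and age group.
- Age group 3 with the sex term: 0.35 + 0.10 = 0.45. Age group 4 without it: 0.45. Same score, different sex and age group.

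**2. How often pairs agree.** Data source gives up to 700 practices and over 5 million active records: 5,000,000 / 700 = about 7,143 per practice. Assumed: 8 age groups, 2 sexes, ethnic shares 86/8/3/2/1%, 5 IMD groups, a main-effects score, 1,500 cases per setting, and controls drawn from a single practice of 500 or 7,143. Tied means that different profiles can share exactly the same score.

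| Pool and method | Sex, all | Age group, all | Ethnicity, all | Ethnicity, non-White cases |
|---|---|---|---|---|
| 500, nearest, tied | 58.5% | 35.2% | 87.9% | 57.7% |
| 500, nearest, no ties | 89.5% | 83.9% | 91.1% | 64.5% |
| 7,143, nearest, tied | 59.7% | 36.2% | 88.4% | 59.3% |
| 7,143, nearest, no ties | 99.3% | 98.9% | 98.9% | 95.0% |
| 7,143, caliper 0.2 SD, tied | 56.2% | 30.7% | 88.3% | 57.4% |
| 7,143, caliper 0.2 SD, no ties | 55.5% | 33.7% | 88.0% | 59.3% |

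Agreement runs from poor to nearly complete according to the algorithm, which the protocol leaves open. It is guaranteed in no setting, and agreement on ethnicity is lower for non-White cases in every row.

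**3. Whether disagreement unbalances the subgroups.** This is a separate question, examined with within-practice 1:1 matching in practices of 7,000 with varying ethnic mix.

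- *Score correctly specified (600 practices, nearest neighbour).* Ethnicity agreed in only 39% of Black, 19% of Mixed and 13% of Other pairs. Yet the strata kept their numbers (cases/controls: Black 1,170/1,171, Mixed 608/598, Other 380/370). Standardised differences in age within ethnic group were 0.06 or less; those in sex and IMD were 0.07 or less, except sex in the smallest group (0.11). With calipers of 0.05 to 0.2 SD, age differences stayed at about 0.10 or below, and the largest IMD difference was 0.15.
- *Same setting, with a true age-by-ethnicity interaction left out of the score.* Age differences in the non-White groups rose to about 0.08 to 0.21.
- *Separate run (150 practices, 60-97% White, incidence by age and sex differing across ethnic groups, main-effects score, caliper 0.05 to 0.2 SD).* Age differences were about 0.09 (Asian), 0.13 (Black), 0.20-0.22 (Mixed) and 0.24-0.27 (Other), against 0.03 or less (White). The sex mix shifted by 3 to 8 percentage points in the minority strata. With strict nearest-neighbour matching and no ties, age differences were about 0.1 or less.

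So broken pairs alone did little harm to balance. Material imbalance appeared mainly when the score omitted an interaction, and in the caliper run it grew as the ethnic group became smaller.

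**The case against.** The strongest reply is that disagreement within pairs is not subgroup bias. Gender and ethnicity are both in the score, and a correctly specified score balances the joint distribution of its variables in expectation, so age, sex and IMD are balanced within each ethnic group too. A case whose control is of another ethnicity is compared with controls selected for other cases, and the stratum is not short of controls. Step 3 bears this out, and the point stands. A reader might infer from low pair agreement that the subgroup odds and hazard ratios compare groups of different age or sex mix, or that minority strata lack controls. The documents do not support either inference.

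It can also be said that calipers, exact-match factors, interaction terms, balance checks and adjustment are usually left to a statistical analysis plan, which is not shown here, and that the protocol's parenthesis could be meant as direct matching on the listed variables. Both are fair, and both limit the point. But the protocol itself names the method and gives one order of preference, practice, without giving gender or ethnicity any priority. That choice settles who enters the dataset. Later adjustment can reduce imbalance, but it cannot restore pairs matched on the subgroup variable.

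Finally, replacing the score with matching on year of birth would be a design preference. The point does not need it.

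**Conclusion.** The point holds in a limited form. As written, a matched pair need not share gender or ethnicity and can be broken in the planned subgroup comparisons. Balance inside those subgroups then depends on the score being correctly specified, including interactions with ethnicity, and is least secure in the small ethnic groups.

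The size is not known. In the simulations, agreement on ethnicity for non-White cases taken together ranged from about 57% to 95%. Age imbalance in non-White groups ran from about 0.1 or less to 0.27, with the larger values arising when an interaction was omitted. These figures rest on assumed practice mix, coefficients and algorithm. No odds or hazard ratio was computed, so nothing here shows that a result by ethnicity would be biased. The case for change is that the stated aim can be protected cheaply, whichever algorithm is chosen.

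**What to change.** In Methods, Study design, state that:

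1. The control must agree exactly with the case on gender and on ethnicity category.
2. Within those strata, the control is chosen on a propensity score for age group and IMD, from the same practice where possible.
3. If the practice has no eligible control of that gender and ethnicity, one is taken from another practice.

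In Statistical methods, add covariate balance checks within each gender and ethnicity subgroup, and adjust the subgroup models for age and IMD.

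Agreement on gender and ethnicity is then 100% by construction, and every pair stays whole in the planned subgroups. The cost is a change to the matching rule before controls are selected; no new data are needed. The downside is that some minority-ethnic cases will have a control from another practice, with some loss of control over practice-level differences in recording and referral. The existing proviso, "matching within primary care practice where numbers allow", already permits that. With more than 5 million active records, few cases should go unmatched, though the protocol gives no counts by ethnicity to confirm it.

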### Primary objectives

- Briefly describe the epidemiology of vitiligo in the dataset: vitiligo incidence of vitiligo over time and by age, sex, ethnicity and sociodemographic factors and lifetime prevalence by age and sex.
- Describe the prevalence of common mental health conditions (depressive episodes, recurrent depressive disorder and anxiety disorder), overall and stratified by sociodemographic factors and location of lesion, in adult patients diagnosed with vitiligo in a contemporary real-world population compared with matched controls without vitiligo
- Describe the incidence of common mental health conditions (depressive episodes, recurrent depressive disorder and anxiety disorders), overall and stratified by sociodemographic factors and lesion location, in adult patients diagnosed with vitiligo in a contemporary real-world population compared with matched controls in the first two years after vitiligo diagnosis.
- Describe current primary care service utilisation (primary care visits) and management patterns (secondary care referrals) in people with vitiligo with and without mental health conditions.

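### Primary care visits recur, but the plan compares them with Cox models and names no count or recurrent-event form; an ordinary Cox model would time the first visit rather than compare visit frequency

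*Protocol*

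**What the plan says.** The fourth primary objective in the protocol is to "Describe current primary care service utilisation (primary care visits) and management patterns (secondary care referrals) in people with vitiligo with and without mental health conditions".

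The service-utilisation paragraph of Study design turns this into two questions about a mental health condition present at diagnosis: "whether this is associated with increased primary care visits or an increased chance of a secondary care referral to dermatology". The groups to be compared and the model are then fixed in one sentence, which sets patients "in those with a depressive illness or anxiety disorder at baseline to those without using Cox proportional hazards models adjusted for sociodemographic factors"; adjustment is to extend to further confounders. The same model is assigned to visits and to referrals, and the window is one year from diagnosis.

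The paragraph ends: "We will also report the overall primary care visit frequency and secondary care referral rate for comparison". The Statistical methods section names effect measures only for the mental health outcomes: "baseline prevalence (odds ratio) and incidence (hazard ratio) for each mental health condition in the vitiligo cases compared with controls".

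**The concern.** The two questions differ in kind. Referral to dermatology is asked as a chance, meaning whether the event happens within the year, and time to first referral in a Cox model answers that. Visits are asked as an amount, meaning whether there are more of them. A patient may consult many times in a year, and a Cox model in its usual form counts only the first event.

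Two things follow for visits.

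- Everything after the first visit is ignored, although the question concerns how many there are.
- If patients differ in their underlying consulting rate, the first-visit hazard ratio is pulled towards 1 relative to the visit rate ratio, increasingly so as the year goes on. Frequent consulters leave the risk set early, and they leave faster in the higher-rate group.

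The adjusted comparison would then give a number that a reader could take for relative visit frequency but that is not one. Its direction would usually be right. Its size would tend to be too small, and a modest difference would be easier to miss.

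**Working it through.** The protocol gives no visit rate, sample size or effect size for this comparison, so there is no figure of its own to reproduce. The mismatch follows from the wording; the calculation only illustrates its possible size.

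**Inputs**

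- From Study design: follow-up of one year after diagnosis; two groups, with and without a depressive illness or anxiety disorder at baseline; Cox model.
- Assumed: share with a condition p = 0.25; whole-cohort mean m = 2, 5 or 8 visits a year; true visit rate ratio R = 1.5 (also 1.2); each patient's constant rate multiplied by a gamma variable with mean 1 and variance θ = 0, 0.5, 1 or 2.

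**Formulas**

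- Group rates: λ0 = m / (1 − p + pR) and λ1 = Rλ0.
- Probability of no visit by time t: S_g(t) = (1 + θλ_g t)^(−1/θ), or exp(−λ_g t) when θ = 0.
- First-visit hazard: h_g(t) = λ_g / (1 + θλ_g t).
- Hazard ratio at time t: R(1 + θλ0 t) / (1 + θλ1 t). This starts at R and falls towards 1 if θ > 0.
- Large-sample Cox estimate: the β that solves ∫ from 0 to 1 of { pS1h1 − [pS1e^β / (pS1e^β + (1 − p)S0)] × (pS1h1 + (1 − p)S0h0) } dt = 0.
- First visits as a share of all visits: [p(1 − S1(1)) + (1 − p)(1 − S0(1))] / m.

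**One case in full (R = 1.5, m = 5, θ = 1)**

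- λ0 = 5 / 1.125 = 4.444 and λ1 = 6.667.
- Hazard ratio at one year = 1.5 × 5.444 / 7.667 = 1.07.
- Cox estimate from the score equation = 1.27, against a true rate ratio of 1.5.
- S0(1) = 1/5.444 = 0.184 and S1(1) = 1/7.667 = 0.130. First-visit share = (0.75 × 0.816 + 0.25 × 0.870) / 5 = 0.17.

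**All cases, R = 1.5**

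| θ | Cox HR at m = 2 / 5 / 8 | Hazard ratio at one year |
|---|---|---|
| 0 | 1.50 / 1.50 / 1.50 | 1.50 / 1.50 / 1.50 |
| 0.5 | 1.37 / 1.33 / 1.33 | 1.21 / 1.12 / 1.08 |
| 1 | 1.31 / 1.27 / 1.25 | 1.14 / 1.07 / 1.04 |
| 2 | 1.25 / 1.21 / 1.19 | 1.08 / 1.03 / 1.02 |

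For θ from 0.5 to 2, first visits make up 9% (m = 8, θ = 2) to 37% (m = 2, θ = 0.5) of all visits.

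**Sensitivity**

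- Setting p to 0.15 or 0.35 moves the Cox hazard ratio by less than 0.01.
- At a mean of one visit a year the Cox hazard ratio is 1.29 to 1.41 for θ from 0.5 to 2.
- Adjusting for a measured predictor of visits (log-SD 0.5), with residual variance 0.5 to 1 and mean 5 visits, still gives 1.28 to 1.35.
- With R = 1.2, m from 2 to 8 and θ from 0.5 to 2, the Cox hazard ratio is 1.08 to 1.15. In simulation with an illustrative 2,000 patients, power was 28% to 68% for first-visit Cox and 58% to 99% for a rate model with robust variance.
- If a baseline condition changes only the rate of visits after the first (unexposed mean 2, 5 or 8, later visits 1.5 times as frequent, θ of 0, 0.5 or 1), simulation gave a ratio of mean counts of 1.27 to 1.46 and a first-visit hazard ratio of 0.99 to 1.01. The difference would not be seen at all.

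**The case against.** The strongest reply is that the protocol does not say first visit. A recurrent-event model of Andersen-Gill type is itself a Cox-type model, and one of the remedies below would be compatible with the present wording. How repeats are handled is often left to the SAP, which is not shown. This stands as a limit: the attenuation applies to the ordinary reading of the text, not to every model that could carry the name. But the protocol is not silent. It names a model, gives the same one to a recurring and a near-single event, and its usual meaning does not answer the visit question. An SAP that followed it literally would carry the mismatch forward.

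Second, visit frequency will also be reported. As written, that is an overall figure. It promises no adjusted contrast between the two groups, so it does not fill the gap, though it gives readers some context.

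Third, the objective is to describe, Study design presents this part as exploratory, and utilisation is not among the outcomes in Table 2. That is fair, and it limits the weight of the point. Visits are nonetheless named in a primary objective.

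Fourth, the numbers rest on assumptions. With no residual variation between patients there is no attenuation. The database may also yield far more than 2,000 cases: scaling the worst-case 28% power by the square root of sample size gives about 59% at 5,000, 87% at 10,000 and 99% at 20,000. So the loss of power may matter little. A larger sample does not remove the attenuation, however; it only estimates the attenuated value more precisely.

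Finally, the Statistical methods section concerns mental health outcomes in cases and controls, so its silence on visits is weak evidence.

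**Conclusion.** The concern holds. The protocol asks whether visits are more frequent and assigns a model that, on its ordinary reading, compares how soon the first visit occurs. This is a stated method that fits its question poorly, not merely a missing detail.

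The size is conditional. With moderate to strong differences between patients in consulting rate (gamma variance 0.5 to 2) and 2 to 8 visits a year, a true rate ratio of 1.5 would appear as 1.19 to 1.37, and 1.2 as 1.08 to 1.15. With no such differences the hazard ratio equals the rate ratio and the cost is lost information only. None of these inputs comes from the protocol except the one-year window and the two groups.

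The point should be fixed. It affects the visit half of one primary objective. The referral comparison and the depression and anxiety comparisons are untouched.

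**What to change.** In the service-utilisation paragraph of Study design, separate the two outcomes.

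- **Visits:** analyse the number of primary care visits in the first year by negative binomial regression with a log person-time offset, or by a recurrent-event rate model such as the Andersen-Gill form with robust variance. Adjust for the same covariates and report an adjusted rate ratio with its 95% confidence interval.
- **Referral:** keep the Cox model and state that the event is the first dermatology referral after diagnosis.

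The cost is about one sentence in the protocol and a different regression command on data already extracted. No new data are needed.

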## Statistical methods

Standard descriptive statistics (mean, standard deviations, etc) will be used to describe the characteristics of the study cohort. The study will report the baseline prevalence (odds ratio) and incidence (hazard ratio) for each mental health condition in the vitiligo cases compared with controls. These outcomes will be compared between cases and controls in subgroups by gender and ethnicity. Within the vitiligo cohort the relationship between disease characteristics and the primary outcomes will be examined. Statistical significance for analyses will be reported using P values and 95% confidence intervals as appropriate.

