In addition to skin colour, the location of vitiligo lesions may also influence the overall well-being and stigmatisation experience of patients. However, inconsistent findings have been reported. A few studies showed that patients had a more significant QoL impairment when lesions were located on visible sites (e.g. face, neck and hand) [10, 11] whilst other studies did not find any relationship [12, 13]. By contrast, some studies report vitiligo lesions on more central body parts (e.g. chest, arms and trunks) are more likely to have an adverse impact on emotional wellbeing of people with the condition, perhaps because there remains anxiety as to how they might be judged by others if the condition were to be revealed [7, 14]. Indeed, the nature of reactions received from others is also likely to play an integral role in adjustment and the extent to which stigmatisation is experienced [15, 16]. Additional data from mixed method studies is needed to further understand this topic and how this may affect the possible comorbid burden of mental health conditions.

There is currently a lack of large population-based studies providing reliable estimates of the risks of psychological comorbidities associated with vitiligo in the UK. A recent observational study using the UK-THIN database [17] highlighted the burden of depression in vitiligo patients and found a bidirectional relationship between the two conditions. However, the study did not explore the associations with other forms of psychological distress and did not use a validated definition for depression. An analysis of the depression risk on the populations of different ethnicity and location of the vitiligo lesions, which can be potential sources of heterogeneity, were also not conducted.

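### The aim is to see whether relative risks vary by ethnicity, but the only analysis named compares cases with controls inside each ethnic group

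*Protocol*

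**What the plan says.** The Objectives section of the protocol gives, as part of the study's aim, "to evaluate whether the relative risks may vary by different ethnicity". The Background prepares for this by noting that, in the earlier UK database study, analyses by "different ethnicity and location of the vitiligo lesions, which can be potential sources of heterogeneity, were also not conducted".

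The listed Primary objectives are worded more softly. They describe prevalence "overall and stratified by sociodemographic factors and location of lesion" and incidence "overall and stratified by sociodemographic factors and lesion location", each compared with matched controls. Study design fixes five ethnic categories: "White, Asian, Black African/Caribbean, Mixed, and Other".

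Statistical methods first gives the main analysis: "The study will report the baseline prevalence (odds ratio) and incidence (hazard ratio) for each mental health condition in the vitiligo cases compared with controls". For ethnicity it then adds one sentence: "These outcomes will be compared between cases and controls in subgroups by gender and ethnicity". On inference it says: "Statistical significance for analyses will be reported using P values and 95% confidence intervals as appropriate".

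**The concern.** Two different questions are in play. One is whether people with vitiligo differ from controls within a given ethnic group. The other is whether the size of that difference depends on ethnicity. The Objectives section asks the second; Statistical methods names an analysis for the first.

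The gap matters because significance inside a subgroup depends on the number of events as well as on the effect. If the true ratio is the same in all five groups, the largest group can easily be significant while the small ones are not. A reader could take that pattern as evidence that vitiligo carries a different psychological risk in different ethnic groups. The Conclusions section expects the results to guide early intervention towards those at highest risk, so a false reading of variation could be acted on.

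**Working it through.** **Text check.** The protocol names three sets of association analyses:

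- cases against controls, overall and in gender and ethnicity subgroups (Statistical methods);
- disease characteristics against the primary outcomes within the vitiligo cohort (Statistical methods);
- service use by mental health status at diagnosis (Study design).

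None compares the case-control ratio of one ethnic group with that of another. No interaction term, heterogeneity test or ratio of ratios appears.

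**Size: inputs.** The protocol gives no sample size, event count, effect size or ethnic mix, so there is no figure to reproduce and every input except the 1:1 matching, the five groups and the two-year window is an assumption. Base case: 10,000 pairs; shares 80/10/5/2/3%; control incidence 4% over two years; the same true hazard ratio (HR) in every group; two-sided 5% tests.

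**Formulas.** For a group of n pairs with incidence p:

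- control events e0 = n × p; case events e1 = n × (1 − (1 − p)^HR);
- SE of log HR = √(1/e0 + 1/e1);
- power = Φ(ln HR/SE − 1.96) + Φ(−ln HR/SE − 1.96).

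**Base case at HR 1.25** (ln HR = 0.223):

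| Share | e0 | e1 | SE | Power |
|---|---|---|---|---|
| 80% | 320 | 398.0 | 0.075 | 0.844 |
| 10% | 40 | 49.7 | 0.212 | 0.183 |
| 5% | 20 | 24.9 | 0.300 | 0.115 |
| 2% | 8 | 9.9 | 0.475 | 0.076 |
| 3% | 12 | 14.9 | 0.388 | 0.089 |

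The chance of a mixed pattern (at least one group significant and at least one not) is 1 − P(none significant) − P(all significant):

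- none: 0.156 × 0.817 × 0.885 × 0.924 × 0.911 = 0.095
- all: 0.844 × 0.183 × 0.115 × 0.076 × 0.089 = 0.0001
- mixed: 1 − 0.095 − 0.0001 ≈ 0.90

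**Range, with no true variation in any row:**

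| Scenario | Mixed pattern |
|---|---|
| Base, HR 1.0 | 23% |
| Base, HR 1.1 | 40% |
| Base, HR 1.25 | 90% |
| Base, HR 2.0 | 88% |
| HR 1.25, incidence 2% / 8% | 69% / 99% |
| HR 1.25, 5,000 / 20,000 pairs | 69% / 99% |
| HR 1.25, shares 60/20/10/5/5% | 88% |
| HR 2.0, shares 60/20/10/5/5%, 20,000 pairs | 11% |
| The same with 50,000 pairs | near 0% |

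Cochran's Q on 4 df, a direct test of equal ratios, rejects in about 5% of simulated studies in every row.

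**Second check, two groups only.** Use power = Φ(|ln HR| × √events / 2 − 1.96). With a common HR of 1.3 and 800 against 80 events, power is 0.960 and 0.216. Exactly one group is significant with probability 0.960 × 0.784 + 0.216 × 0.040 ≈ 0.76. Over HR 1.2 to 1.5 and event pairs 800/80, 800/200 and 400/40, this runs from 18% to 76%.

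**What a direct contrast can deliver.** Base case at HR 1.25, each group against the largest. SE of the log ratio = √(SE_group² + SE_largest²); 95% CI if there is no true difference = exp(±1.96 × SE); ratio detectable with 80% power = exp(2.80 × SE).

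| Share | SE | 95% CI | Detectable ratio of HRs |
|---|---|---|---|
| 10% | 0.225 | 0.64–1.56 | 1.9 |
| 5% | 0.310 | 0.55–1.84 | 2.4 |
| 3% | 0.395 | 0.46–2.17 | 3.0 |
| 2% | 0.481 | 0.39–2.57 | 3.8 |

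**The case against.** The strongest reply is that this is detail for a statistical analysis plan. Statistical methods is one short paragraph, and an interaction term is the kind of thing a later plan adds. The subgroup ratios with confidence intervals are also the raw material for judging variation, and the listed Primary objectives ask only for stratified description. Nothing in the protocol says that variation will be inferred from which groups are significant, so the mixed-pattern rates are not error rates of the plan as written. They become so only if someone reads the results that way.

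Much of this is fair. The stratified estimates do meet the descriptive objectives, and the percentages measure an exposure to misreading, not a certain error. But the point is not only a missing detail. The Objectives section states an effect-modification aim, and the one analysis that the protocol assigns to ethnicity addresses another question. A later plan could repair that, but this document does not call for it.

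Two technical points also stand. With 8 expected control events in the smallest group, the normal approximation is rough; with Poisson event counts the Q test rejects in just under 4% of studies, which is conservative and not harmful. The gap between 84% and 18% power in the two largest groups makes the case without the smallest one. Second, a non-significant 4-df test could itself be misread as proof of no variation. For that reason the ratios and their intervals should carry the interpretation.

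**Conclusion.** The concern holds. The protocol states an aim about variation of relative risks by ethnicity and names no analysis that addresses it. If variation were read from within-group significance, a false impression would arise in about 23% to 90% of studies in the base case, depending on the common HR. Across all scenarios tried, the range is near 0% to 99%. These figures rest on assumed pairs, incidence, shares and HRs; the mismatch between aim and analysis does not. It should be fixed, but it touches one aim and leaves the overall case-control comparison intact.

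**What to change.** Add to Statistical methods:

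> Variation by ethnicity in the primary outcomes (depression, anxiety) will be assessed with a vitiligo × ethnicity interaction (4 df) in the OR and HR models. Ratios of ORs and HRs between ethnic groups will be reported with 95% CIs beside the subgroup estimates. Differences in significance between subgroups will not be taken as evidence of variation, and a non-significant interaction will not be taken as evidence of no variation.

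The same may be done for gender (1 df) as a secondary check. If the sponsor intends description only, the alternative is to reword the aim in Objectives to match the Primary objectives; the caution about significance patterns should still be added.

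The cost is a few sentences and one interaction term per primary-outcome model, with no change to design, matching or data extraction. The drawback is low power in small groups: the detectable ratios of about 1.9 to 3.8 shown above mean that only large differences could be established there.
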